3 STUDY OVERVIEW

3.1 Overall Study Design and Methodology

3.1.1 *Study Design*

This is a Phase 1, first in human study of ChAdOx1-HBV. The study will be conducted in 40 healthy participants and 12 participants with CHB and virally suppressed with oral antiviral medication. This will be an open-label, non-randomised dose escalation study comparing the safety, tolerability and immunogenicity of 2 different doses of ChAdOx1-HBV vaccine. T cell responses in healthy participants who have received a prior two-dose series of AZD1222 or at least two doses of the Pfizer or Moderna mRNA COVID-19 vaccines will also be analysed. The study design is shown in [Figure 2](#).

Figure 2 Overall Study Design

Abbreviations: ChAdOx1-HBV=chimpanzee adenovirus-vectored hepatitis B virus vaccine; CHB=chronic hepatitis B virus; HD=high dose; LD=low dose; N=number of participants; vp=viral particles

Five reviews of the safety, tolerability and available immunogenicity data will be performed by a Safety Monitoring Committee (SMC):

- First review: at least 48 hours after the first healthy participant has received the first low dose of ChAdOx1-HBV vaccine. This review will occur *before* dosing the remaining participants in cohort 1
- Second review: at least 48 hours after the last healthy participant has received the last low dose of ChAdOx1-HBV vaccine. This review will occur *before* dosing high dose healthy participants in cohort 2
- Third review: at least 48 hours after the last healthy participant has received the last high dose of ChAdOx1-HBV vaccine. This review will occur *before* dosing low dose CHB participants in cohort 3

- Fourth review: at least 48 hours after the first CHB participant has received the first low dose of ChAdOx1-HBV vaccine. This review will occur *before* dosing the remaining participants in cohort 3
- Fifth review: at least 48 hours after the last participant with CHB has received the low dose of ChAdOx1 HBV vaccine cohort 3 *before* dosing high dose CHB participants in cohort 4

No SMC review is required for cohorts 5 and 6 as the dose administered has been assessed in the previous cohorts of healthy participants.

A Data Monitoring Committee (DMC) will be appointed to perform unscheduled reviews of the available data including safety and tolerability study data and make recommendations concerning the continuation, modification or termination of the study if one of the study stopping or holding rules defined in [Section 3.1.3](#) is met.

3.1.2 *Study Methodology*

Participants will be screened in the period Day -42 to Day -1. Informed consent will be obtained before any study specific procedures are performed. Eligible participants will then attend the clinic to receive study vaccine on Day 0. Participants will be enrolled sequentially.

The study will investigate response to study vaccine as shown in [Table 2](#). On Day 0, an electronic diary (eDiary), tape measure and thermometer will be provided to perform self-assessment of local and systemic reactogenicity. All participants will then have a follow-up telephone call on Day 1 and return to the clinic for study assessments on Days 7, 14, 28, 84. Participants in cohorts 1-4 only, will also have follow up visits on Day 56 and Day 168. End of study visit procedures will be performed at the final visit.

Five healthy participants will be administered the low dose first (cohort 1). Dose escalation will only be initiated in the next 5 healthy participants (cohort 2) following SMC review.

Six CHB participants will be administered the low dose (cohort 3) before the dose escalation is initiated in the remaining 6 CHB participants (cohort 4).

Thirty healthy participants (15 who have received two doses of AZD1222 [cohort 5] and 15 who have received at least two doses of either Pfizer or Moderna mRNA COVID-19 vaccine [cohort 6]) will be dosed in parallel with the high dose used in cohorts 2 and 4.

The first participant in each of cohorts 1-4 will be assessed for 1 hour in the clinic post-vaccination in case of immediate adverse events (timed after the end of study vaccine administration). All other participants will be assessed for 30 minutes.

The safety and immunogenicity assessments to be performed in cohorts 1-4 are:

- Haematology (full blood count, haemoglobin, haematocrit, erythrocytes, mean cell volume, mean corpuscular haemoglobin, mean corpuscular haemoglobin concentration, leukocytes, neutrophils, lymphocytes, monocytes, eosinophils, basophils, fibrinogen, prothrombin time [PT] and international normalised ratio [INR], activated partial thromboplastin time [aPTT] and platelets) will be analysed at screening, pre-vaccination on Day 0 and on Days 7, 14, 28, 56, 84 and 168
- Biochemistry (sodium, potassium, urea, creatinine and albumin) will be analysed at screening, pre-vaccination on Day 0 and on Days 7, 14, 28, 56, 84 and 168
- Liver function tests (LFTs; alkaline phosphatase [ALP], gamma-glutamyl transpeptidase [GGT], alanine transaminase [ALT], aspartate transaminase [AST] and

total bilirubin) will be analysed at screening, pre-vaccination on Day 0 and on Days 7, 14, 28, 56, 84 and 168

- HBV disease markers in serum:
 - Healthy participants: qualitative HBsAg will be tested at screening, hepatitis B surface antibody (HBsAb) and HBcAb will be tested at Day 0, and repeated at the end of the trial if negative at baseline, or at discretion of the Investigator
 - CHB participants: HBV DNA and quantitative HBsAg will be tested at screening and repeated on Days 0, 28, 56, 84 and 168. The following parameters will also be analysed on days 0, 28, 56, 84 and 168: HBeAg, HBcAg, anti-HBs, anti-HBe, anti-HBc, pgRNA
- A full physical examination will be performed at screening and pre-vaccination on Day 0. A symptom-directed physical examination will be performed on Days 7, 14, 28, 56, 84 and 168
- Vital signs will be performed at screening, pre-vaccination and post-vaccination at the on Day 0 and on Days 7, 14, 28, 56, 84 and 168
- Local and systemic reactogenicity (pain, induration, warmth, erythema at the vaccination site plus feverishness, chills, myalgia, fatigue, headache, nausea, arthralgia, malaise) will be captured pre-vaccination and post-vaccination on Day 0 and by eDiary for 3 days post-vaccination
- Unsolicited adverse events will be recorded in the eCRF from the date the informed consent is signed, at all clinic visits to cover the period since the previous visit and during the visit and up to 28 days post-vaccination
- Serious adverse events (SAEs) and adverse events of special interest (AESIs) will be recorded from the date the informed consent is signed until the end of the study and or resolved or until participant contact discontinues
- Cellular immune responses will be measured in peripheral blood mononuclear cells (PBMCs) samples taken on pre-vaccination on Day 0 and on Days 14, 28, 56, 84 and 168. Samples will be analysed by ICS

For participants in cohorts 5 and 6, all assessments on Days 0, 7, 14, 28 and 84 above will be performed. In addition, neutralising antibodies to ChadOx1 will be assessed on Days 0 and 84.

In CHB participants who consent to LFNA, these will be taken pre-vaccination within the screening period and at the clinic visit on Day 84. Liver fine needle aspirate assays may be used to quantify and characterise intrahepatic immune and parenchymal cells and/or HBV DNA and RNA transcripts. These aspirates and subsequent LFNA assessments are optional.

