3.1.3 Study Stopping Criteria/Holding Criteria/Dose Escalation Process

There will be a review of the study data by the DMC when there is a reasonable possibility that the investigational vaccine caused any of the listed following adverse events based on the assessment of the Investigator in one or more participants at any dose. Vaccinations will be held pending this review:

- Death
- Life-threatening adverse event or life-threatening suspected reaction
- Serious suspected adverse reaction

- Suspected, unexpected, serious adverse reaction (SUSAR)
- Acute allergic reaction or anaphylactic shock following the administration of vaccine investigational product
- Anaphylaxis or bronchospasm, indicative of an immediate hypersensitivity reaction to study vaccine
- If any participant has any of the following:
 - ALT or AST >8 x upper limit of normal (ULN)
 - ALT or AST >5 x ULN for more than 2 weeks
 - ALT or AST >3 x ULN and (total bilirubin >2 x ULN or INR >1.5)
 - ALT or AST >3 x ULN with the appearance of fatigue, nausea, vomiting, right upper quadrant pain or tenderness, fever, rash, and/or eosinophilia (>5%)

The competent authority and Research Ethics Committee (REC) will be notified of a temporary halt within 15 days according to the local requirements. If, following the review of data, a recommendation is made by the DMC to resume study enrolment and vaccine administration, the DMC will record their judgment in a memorandum to the study file and notify the Sponsor. The DMC memorandum will be forwarded to the local Medical Monitor and Investigators.

3.1.4 *Duration of Study*

3.1.4.1 *Duration for Each Participant*

Cohorts 1-4: Up to 8 months (up to 1.5 months for screening and 6.5 months on the study with study vaccine given on Day 0).

Cohorts 5 and 6: Up to 4.5 months (up to 1.5 months for screening and 3 months on the study with study vaccine given on Day 0).

3.1.4.2 *Duration of Study*

It is planned that the study will take 16 months to implement, enrol and read out.

The end of the study is defined as the date of database lock.

3.2 *Discussion of Study Design*

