8 SAFETY MANAGEMENT

8.1 Responsibilities for Ensuring the Safety of Study Participants

The national Competent Authority, the study Sponsor, the Institution through which the research is performed, and all members of the Investigator's study team share responsibility for ensuring that participants in this study are exposed to the least possible risk of adverse events that may result from participation in this protocol.

8.1.1 *Investigator*

The Investigator has a personal responsibility to closely monitor study participants and an inherent authority to take whatever measures necessary to ensure their safety. The Investigator may delay a participant's study vaccine administration or pause study vaccine administration in the whole study if they have some suspicion that the study vaccine might place a participant at significant risk. The Investigator determines severity and causality for each adverse event.

Responsibilities of the Investigator may be assigned to a designee who is a medically qualified study team member, however the accountability for the specific task remains with the Investigator.

8.1.2 *Study Sponsor*

The Sponsor also has an institutional responsibility to ensure participant safety. This responsibility is vested in the local Medical Monitor and an SMC.

8.1.3 *Local Medical Monitor*

The local Medical Monitor (LMM) is the Sponsor's medical representative. The LMM reviews safety information collected throughout the study. The LMM can add another causality to the Investigator's causality assessment, however the causality assessment given by the Investigator must not be downgraded by the LMM. If the LMM disagrees with the Investigator's causality assessment, the opinion of both the Investigator and the Sponsor should be provided with the report.

8.1.4 *Safety Monitoring Committee*

The SMC will constitute the Sponsor Representative, the Principal Investigator at each centre, the local Medical Monitor and the Chief Investigator. The SMC will operate in accordance with the study-specific charter, which will be agreed prior to the start of enrolment.

An SMC will be appointed to review the study data and make recommendations concerning the continuation, modification, or termination of the study. The SMC will perform the following:

- Scheduled evaluation of study conduct, progress and review of the safety data. Scheduled meetings will take place as follows:
 - Kick off meeting before the first participant is enrolled

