 - At least 48 hours after the first healthy participant is dosed in cohort 1
 - At least 48 hours after cohort 1 dosing is complete
 - At least 48 hours after cohort 2 dosing is complete
 - At least 48 hours after the first CHB participant is dosed in cohort 3
 - At least 48 hours after cohort 3 dosing is complete

- The SMC will be notified within 24 hours of the Investigators' being aware of any severe local or systemic reaction or vaccine-related SAE. If a severe local or systemic reaction or vaccine-related SAE occurs at any time point during the study, the SMC will review the case immediately.
- The SMC will be convened if any of the stopping or holding rules are met (see [Section 3.1.3](#))

The SMC has the power to place the study on hold if deemed necessary

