- First review: at least 48 hours after the first healthy participant has received the first low dose of ChAdOx1-HBV vaccine. This review will occur before dosing the remaining participants in cohort 1
- Second review: at least 48 hours after the last healthy participant has received the last low dose of ChAdOx1-HBV vaccine. This review will occur before dosing high dose healthy participants in cohort 2
- Third review: at least 48 hours after the last healthy participant has received the last high dose of ChAdOx1-HBV vaccine. This review will occur before dosing low dose CHB participants in cohort 3
- Fourth review: at least 48 hours after the first CHB participant has received the first low dose of ChAdOx1-HBV vaccine. This review will occur before dosing the remaining low dose CHB participants in cohort 3
- Fifth review: at least 48 hours after the last participant with CHB has received the low dose of ChAdOx1-HBV vaccine cohort 3 before dosing high dose CHB participants in cohort 4

A Data Monitoring Committee (DMC) will be appointed to perform unscheduled reviews of the available safety and tolerability study data and make recommendations concerning the continuation, modification or termination of the study if one of the study stopping or holding rules is met.

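### The fifth SMC review can open the ten-fold dose in CHB 48 hours after the last low dose, before that participant has any scheduled post-dose liver test

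*Protocol*

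**What the plan says.** Cohort 3 (six CHB participants, 2.5×10^9 vp) is dosed before cohort 4 (six CHB participants, 2.5×10^10 vp). Two SMC reviews govern this part of the study.

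- The fourth releases the other five low-dose participants: "Fourth review: at least 48 hours after the first CHB participant has received the first low dose of ChAdOx1-HBV vaccine" (protocol 3.1.1).
- The fifth releases cohort 4: "Fifth review: at least 48 hours after the last participant with CHB has received the low dose" (protocol 3.1.1). SAP section 6 words it as "Fifth review: at least 48 hours after the last participant with CHB has received the low dose of ChAdOx1-HBV vaccine cohort 3", and protocol 8.1.4 as "At least 48 hours after cohort 3 dosing is complete".

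In each place the condition is elapsed time alone. No LFT result or complete diary is required.

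LFTs are scheduled at screening, before the dose on Day 0, and then from Day 7 (protocol 3.1.2), with a window of one day either side (Table 2). The Day 1 contact is a telephone call about the diary, without a blood sample (6.3.1). Reactions are entered in the diary on Days 1, 2 and 3 (SAP 10.8.2).

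Protocol 3.2 explains that the low dose comes first in CHB to reduce the risk of liver toxicity from vaccine-induced immune responses, and that the higher dose follows a safety review.

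**The concern.** The reason for the dose sequence and the gate between its two steps do not match. Low-first dosing in CHB is meant to show whether the vaccine provokes liver injury in people whose liver carries HBV. The healthy cohorts cannot show this, because HBsAg-positive people are excluded from them. Yet the rule for moving to ten times the dose can be met before the last low-dose participant has had liver enzymes measured at any scheduled visit. A silent ALT rise in that participant would be unknown to the committee when it decides. No SMC review is scheduled between the first and the remaining cohort 4 participants, so the fifth review is the last planned check before all six high-dose CHB vaccinations.

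**Working it through.** The only figure in the plan here is the 48-hour minimum, so there is no sample size or power to reproduce. The check sets that floor against the visit schedule.

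**Step 1: the last participant.** 48 hours is Day 2. The Day 3 diary entry falls at about 72 hours, 72 − 48 = 24 hours later. The first LFT falls between 6 × 24 = 144 hours and 8 × 24 = 192 hours. That is 144 − 48 = 96 to 192 − 48 = 144 hours later, or 4 to 6 days. Neither can be in hand at the floor. The dose step is 2.5×10^10 / 2.5×10^9 = 10.

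**Step 2: the cohort.** The protocol sets no dosing interval within cohort 3, so pace is an assumption. Let the first participant be dosed on day 0 and the fourth review fall on day 2. Let the other five be equally spaced over *e* days from day 2. The earliest fifth review is day *e* + 4. Days since dose at that review are *e*+4, *e*+2, 0.75*e*+2, 0.5*e*+2, 0.25*e*+2 and 2. An LFT counts as drawn if this is at least 6, 7 or 8; a diary counts as complete if it is at least 3.

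| *e* (days) | Days since dose | LFT drawn, Day 6/7/8 visit | Diary complete |
|---|---|---|---|
| 0 | 4, 2, 2, 2, 2, 2 | 0/0/0 of 6 | 1 of 6 |
| 4 | 8, 6, 5, 4, 3, 2 | 2/1/1 | 5 |
| 14 | 18, 16, 12.5, 9, 5.5, 2 | 4/4/4 | 5 |
| 21 | 25, 23, 17.75, 12.5, 7.25, 2 | 5/5/4 | 5 |
| 28 | 32, 30, 23, 16, 9, 2 | 5/5/5 | 5 |

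At 14 to 28 days, one or two of six lack an LFT. The count is never six of six at the floor. Requiring results rather than draws, with an assumed 2 days of turnaround, gives 4/4/3, 4/4/4 and 5/5/4 for *e* = 14, 21 and 28.

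**Step 3: high doses given before the last low-dose LFT.** That LFT is drawn 4, 5 or 6 days after the review. Suppose cohort 4 starts at the review and doses one participant every *e*/4 days.

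- *e* = 14 (every 3.5 days): doses on days 0 and 3.5, so 2/2/2.
- *e* = 21 (every 5.25 days): doses on days 0 and 5.25, so 1/1/2.
- *e* = 28 (every 7 days): dose on day 0, so 1/1/1.

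If cohort 4 starts about 4 to 6 days after the review, the count is zero.

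**Step 4: information lost.** For an assumed true rate *p* of LFT abnormality, the chance of seeing at least one among *n* tested is 1 − (1 − *p*)^*n*. At *p* = 10% it is 47% with six, 41% with five and 34% with four. At *p* = 20% it is 74%, 67% and 59%.

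**The case against.** The strongest reply is that 48 hours is a minimum and other protections surround it. The committee may wait, and "The SMC will operate in accordance with the study-specific charter, which will be agreed prior to the start of enrolment" (8.1.4); that charter could hold a minimum data package. Entry is limited to well-controlled patients without advanced fibrosis or cirrhosis. Cohort 2 has already had the high dose. The SMC is told within 24 hours of the Investigators' "being aware of any severe local or systemic reaction or vaccine-related SAE", reviews such cases immediately and can halt the study. If an ALT/AST rule in 3.1.3 is met and judged possibly vaccine-related, "Vaccinations will be held pending this review". Unscheduled visits and extra tests are possible, and participants are told to report problems between visits.

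These points limit the size of the gap but do not close it. The enzyme rules cannot act before blood is drawn. Extra tests are discretionary and prompted by an adverse event, so a symptomless rise would not trigger one. None of these provisions requires an LFT in every low-dose CHB participant before escalation.

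It is also fair to say that Day 7 is chosen because it is already scheduled. Nothing in the documents shows that an immune-mediated flare would be visible by then. The first post-dose cellular sample is at Day 14, and one holding rule needs more than two weeks of elevation. A Day 7 condition secures a first look, not a full one.

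Two stronger readings should be set aside. A reader might infer that the fourth review also opens the ten-fold dose. It does not; it releases only further low doses. A reader might also infer that escalation would proceed with no low-dose liver data at all. That needs the last five participants to be dosed within about 2 to 4 days, which is unlikely when "Participants will be enrolled sequentially" (3.1.2).

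**Conclusion.** The point stands as a cheap improvement to the escalation gate. That the last cohort 3 participant lacks a scheduled post-dose LFT and a Day 3 entry at the 48-hour floor follows from the documents and needs no assumption. The cohort figures, one or two of six without an LFT, rest on equal spacing and an assumed 14 to 28 days. The one or two early high-dose vaccinations rest further on a review held exactly at the floor, an immediate start to cohort 4 and an unchanged pace, so they are an upper-end scenario. Whether a gap existed in practice depends on the charter and on when the committee met, neither of which the documents show.

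**What to change.** In protocol 3.1.1, 8.1.4 and the synopsis, with SAP section 6 and the charter aligned, keep 48 hours as the minimum and add one condition for the fifth review: the completed Day 1–3 diaries and the Day 7 LFT results of all six cohort 3 participants must be available.

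Against the floor the delay is (6 to 8) − 2 = 4 to 6 days, or 5 to 8 days with an assumed 1 to 2 days of laboratory turnaround. Of a planned 16 months (about 487 days), 5/487 to 8/487 is 1.0% to 1.6%. The delay is shorter if the committee would have met later anyway. No visit, test or participant is added.

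Two options go further. A Day 14 condition would cost (13 to 15) − 2 = 11 to 13 days before turnaround. A matching condition for the fourth review (the first CHB participant's Day 7 LFT before the other five low doses) would add a similar 4 to 6 days, but is not needed to protect the escalation step.

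The documents do not say whether cohorts 3 and 4 have been dosed. If cohort 4 has, the remedy is one paragraph in the CSR stating which cohort 3 LFT and diary data the fifth review held. If the charter already sets this condition, copying it into the protocol is enough.

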3.1.3 Study Stopping Criteria/Holding Criteria/Dose Escalation Process

There will be a review of the study data by the DMC when there is a reasonable possibility that the investigational vaccine caused any of the listed following adverse events based on the assessment of the Investigator in one or more participants at any dose. Vaccinations will be held pending this review:

- Death
- Life-threatening adverse event or life-threatening suspected reaction
- Serious suspected adverse reaction

- Suspected, unexpected, serious adverse reaction (SUSAR)
- Acute allergic reaction or anaphylactic shock following the administration of vaccine investigational product
- Anaphylaxis or bronchospasm, indicative of an immediate hypersensitivity reaction to study vaccine
- If any participant has any of the following:
 - ALT or AST >8 x upper limit of normal (ULN)
 - ALT or AST >5 x ULN for more than 2 weeks
 - ALT or AST >3 x ULN and (total bilirubin >2 x ULN or INR >1.5)
 - ALT or AST >3 x ULN with the appearance of fatigue, nausea, vomiting, right upper quadrant pain or tenderness, fever, rash, and/or eosinophilia (>5%)

The competent authority and Research Ethics Committee (REC) will be notified of a temporary halt within 15 days according to the local requirements. If, following the review of data, a recommendation is made by the DMC to resume study enrolment and vaccine administration, the DMC will record their judgment in a memorandum to the study file and notify the Sponsor. The DMC memorandum will be forwarded to the local Medical Monitor and Investigators.

3.1.4 *Duration of Study*

3.1.4.1 *Duration for Each Participant*

Cohorts 1-4: Up to 8 months (up to 1.5 months for screening and 6.5 months on the study with study vaccine given on Day 0).

Cohorts 5 and 6: Up to 4.5 months (up to 1.5 months for screening and 3 months on the study with study vaccine given on Day 0).

3.1.4.2 *Duration of Study*

It is planned that the study will take 16 months to implement, enrol and read out.

The end of the study is defined as the date of database lock.

3.2 *Discussion of Study Design*

This is a first in human study of the ChAdOx1 vaccine and is designed to assess the safety in both healthy adults, as well as in the target CHB population. As T cell responses to natural infection are blunted or exhausted in participants with CHB, it will be important to determine how responses in CHB compare to healthy participants. Given the uncertainty around prior use of a vectored vaccine resulting in anti-vector responses, this study will also assess the response of healthy participants who have previously received AZD1222 to ChAdOx1-HBV.

In CHB participants, low dose of the vector (selected based on doses given in a large number of other studies (NCT03399578, NCT03203421, NCT01818362, NCT01623518 and NCT03815942), will first be evaluated to minimise the risk that immune responses generated by vaccination do not result in liver toxicity. To further minimise this likelihood, only those participants whose DNA levels are well controlled on antivirals will be included in the study, and those with advanced liver fibrosis or cirrhosis will be excluded. After safety review, a higher dose, but one shown to be safely used in many other ChAdOx1 studies (HIV, malaria, influenza, MERS), will then be given. Dose selection for future studies will be based on safety

and the induction of T cell activity, as measured by both magnitude of response as well as functionality.

Hepatitis B biomarkers will be evaluated as the basis for future comparison and to assess potential efficacy.

The study will be used as a first step prior to the evaluation of a combination vaccine approach using ChAdOx1-HBV combined with both a MVA encoding the same genetic insert, with or without a low dose PD-1 inhibitor.

